6.2.2.2 Recording of Adverse Events

AEs should be collected and recorded for each patient from the date of the first dose of study drug until the end of their participation in the study, including the safety follow up period.

AEs may be volunteered spontaneously by the study patient, or discovered by the study staff during physical examinations or by asking an open, nonleading question such as 'How have you been feeling since you were last asked?' All AEs and any required remedial action will be recorded on the Adverse Events eCRF and Safety Adverse Event Form. The details of the AE, date of AE onset, date of AE outcome, and action

taken for the AE will be documented together with the principal investigator's assessment of the seriousness of the AE and causal relationship to the study drug and/or the study procedure.

All AEs should be recorded individually, using diagnostic terms where possible. If the diagnosis is not established, individual symptoms may be reported. The AEs will subsequently be coded using the Medical Dictionary for Regulatory Activities (MedDRA).

6.2.2.3 Severity of Adverse Events

Each AE will be assessed by the principal Investigator according to the National Cancer Institute Common Terminology Criteria for Adverse Events (NCI CTCAE), version 4.03 criteria.⁴¹ When changes in the severity (grade) of an AE occur more frequently than once a day, the maximum severity for the event should be noted for that day. Any change in severity of signs and symptoms over a number of days will be captured by recording a new AE, with the amended severity grade and the date (and time, if known) of the change.

6.2.2.4 Causality of Adverse Events

The principal Investigator will assess the causal relationship between BOS161721 or placebo and the AE. One of the following categories (Table 3) should be selected based on medical judgment, considering the definitions below and all contributing factors.

Table 3. Causality Definitions

Related	A clinical event, including laboratory test abnormality, occurs in a plausible time relationship to treatment administration and which concurrent disease or other drugs or chemicals cannot explain. The response to withdrawal of the treatment (dechallenge ^a) should be clinically plausible. The event must be definitive pharmacologically or phenomenologically, using a satisfactory rechallenge ^b procedure if necessary
Unrelated	A clinical event, including laboratory test abnormality, with little or no temporal relationship with treatment administration. May have negative dechallenge and rechallenge information. Typically explained by extraneous factors (e.g., concomitant disease, environmental factors, or other drugs or chemicals)

^a Dechallenge: Upon discontinuation of a drug suspected of causing an AE, the symptoms of the AE disappear partially or completely, within a reasonable time from drug discontinuation (positive dechallenge), or the symptoms continue despite withdrawal of the drug (negative dechallenge). Note that there are exceptions when an AE does not disappear upon discontinuation of the drug, yet drug relatedness clearly exists (for example, as in bone marrow suppression, fixed drug eruptions, or tardive dyskinesia)

^b Rechallenge: Upon re-administration of a drug suspected of causing an AE in a specific patient in the past, the AE recurs upon exposure (positive rechallenge), or the AE does not recur (negative rechallenge)

An unexpected adverse drug event is any adverse drug event for which the specificity or severity is not consistent with the current IP.

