	
 To assess safety, tolerability, and immunogenicity of repeat doses of BOS161721 (20, 60, and 120 mg) administered SC in adult patients with moderately to severely active SLE on limited background standard of care treatment, in order to estimate the optimal dose 	
Safety Endpoints
 
 Incidence and severity of adverse events (AEs) and serious adverse events (SAEs), related AEs, AEs leading to study drug discontinuation, AEs by severity and relatedness Injection site reactions Columbia Suicide Severity Rating Scale (C-SSRS) 12-lead electrocardiograms (ECGs) parameter results at each visit and change from baseline Vital signs (blood pressure [BP], heart rate, and temperature) parameter results at each visit and change from baseline Clinical laboratory results and change from baseline Physical examinations changes from baseline Anti-drug antibodies (ADAs) Study drug exposure/compliance

Secondary	

 To characterize the PK of BOS161721 and select the optimal dose of BOS161721 based on safety, PK, and PD effects in patients with moderately to severely active SLE 	
Pharmacokinetic Endpoints
 
 BOS161721 concentration by visit and time point Maximum observed concentration (C_{max}), first time to maximum concentration (T_{max}), area under the concentration-time curve (AUC), $t_{1/2}$, systematic clearance (CL), volume of distribution (V_d) 
Pharmacodynamic Endpoints
 
 Results and changes (or shifts) from baseline to each visit in phosphorylated signal transducer and activator of transcription 3 (pSTAT3), C3 and C4 levels, and leukocyte immunophenotype Results and changes (or shifts) from baseline in anti-double-stranded DNA (dsDNA), antinuclear antibodies (ANA), anti-Sjögren syndrome A and B (SSA, SSB), Smith (Sm), and antiphospholipid (APL) autoantibodies at each visit Results and changes (or shifts) from baseline in abrogation of IL-21 gene signature at each indicated visit
Exploratory	

 CCI [REDACTED] 	
 CCI [REDACTED]

	
 • CCI [REDACTED] 	
 • CCI [REDACTED] 						
	
 • CCI [REDACTED] 	
 • CCI [REDACTED] 						

POC Phase 2
								

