Blood samples were collected at every in-house study visit for BOS161721 concentration determinations. Blood samples were also collected for determination of IL-21 plasma levels (free and total). Safety was assessed based on the occurrence of treatment-emergent AEs, hepatic function abnormality, and acute and delayed hypersensitivity reactions. Other safety variables included ECGs, vital signs (blood pressure [BP], heart rate, and temperature), safety laboratory assessments, blood sampling for ADAs, total IgG and immunoglobulin M (IgM) levels, CD4+ count, and full and targeted physical examinations. Overall, there were no clinically significant findings from this study. Adverse events reported as related to the study drug, particularly infections, were expected for the compound, and there were no clinically relevant changes in laboratory and ECG results or vital signs. There was 1 serious adverse event (SAE; death due to pulmonary embolism) that occurred 127 days after a single administration of 240 mg SC dose of BOS161721. The causality of this single SAE was not attributed to study drug and further information can be found in the Investigator's Brochure. Final PK data from the SAD study demonstrates BOS161721 has a mean $t_{1/2}$ ranging from 80 to 87 days for doses of ≥ 30 mg in healthy subjects.

[figure not shown]

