6.2.2.7.1 Reporting of Pregnancy

As information is available, a pregnancy diagnosed during the study will be reported within 24 hours to the sponsor via the Pregnancy Notification and Outcome Form, including pregnancy in female patients who received study drug and female partners of male study patients who received study drug. The pregnancy should be followed to term and/or outcome and this outcome should also be reported to the sponsor via the Pregnancy Notification and Outcome Form. Pregnancy itself is not regarded as an AE or SAE unless there is complication.

In the case of a live birth, the structural integrity of the neonate can be assessed at the time of birth. In the event of a termination, the reason(s) for termination should be specified and, if clinically possible, the structural integrity of the terminated fetus should be assessed by gross visual inspection (unless pre-procedure test findings are conclusive for a congenital anomaly and the findings are reported).

If the outcome of the pregnancy meets the criteria for an AE or SAE (i.e., ectopic pregnancy, spontaneous abortion, intrauterine fetal demise, neonatal death, or congenital anomaly [in a live born, a terminated fetus, an intrauterine fetal demise, or a neonatal death]), the Investigator should follow the procedures for reporting SAEs.

Additional information about pregnancy outcomes that are reported as SAEs follows:

- Spontaneous abortion includes miscarriage and missed abortion
- Neonatal deaths that occur within 1 month of birth should be reported, without regard to causality, as SAEs. In addition, infant deaths after 1 month should be reported as serious adverse events when the Investigator assesses the neonatal death as related or possibly related to exposure to investigational product.

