6.2.2.7.2 Reporting of Serious Adverse Events

The principal Investigator is responsible for providing notification to the sponsor of any SAE via the Safety Adverse Event Form, whether deemed study drug related or not, that a patient experiences during their participation in this study within 24 hours of becoming aware of the event.

If an SAE is fatal or life threatening, notification to the sponsor must be made aware immediately, irrespective of the extent of available AE information. This timeframe also applies to additional new information (follow-up) on previously forwarded SAE reports as well as to the initial and follow-up reporting of exposure during pregnancy and exposure via breastfeeding cases. In the rare event that the Investigator does not become aware of the occurrence of an SAE immediately (e.g., if an outpatient study patient initially seeks treatment elsewhere), the Investigator is to report the event within 24 hours after learning of it and document the time of his/her first awareness of the AE.

The principal Investigator will review each SAE and evaluate the intensity and the causal relationship of the event to the study drug. All SAEs will be recorded from the time of first dose of study drug through the safety follow-up period (up to Day 270).

SAEs occurring after the final follow-up visit and coming to the attention of the principal Investigator must be reported only if there is (in the opinion of the principal Investigator) reasonable causal relationship with the study drug.

As a minimum requirement, the initial notification should provide the following information:

- Study number
- Patient number
- Details of the SAE (verbatim details are sufficient for immediate notification)
- Criterion for classification as ‘serious’
- Causality assessment (which may be updated in a follow-up report when sufficient information is available to make this classification)

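### Table 3's two causality categories leave a gap: a plausibly timed event that lupus or background therapy could also explain meets neither definition, so related-AE counts may be too low and will depend on the site

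*Protocol*

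**What the plan says.** Section 6.2.2.4 instructs the investigator as follows: "One of the following categories (Table 3) should be selected based on medical judgment, considering the definitions below and all contributing factors". Table 3 has two rows.

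- **Related.** The event has plausible timing and is one "which concurrent disease or other drugs or chemicals cannot explain". The response to withdrawal ought to be clinically plausible. The row then adds "The event must be definitive pharmacologically or phenomenologically", with rechallenge if needed.
- **Unrelated.** The event is one "with little or no temporal relationship with treatment administration". Two descriptive sentences follow: withdrawal and re-exposure information may be negative, and extraneous factors such as concomitant disease or other drugs are the typical explanation.

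Footnote a to the table accepts that relatedness can be clear even when an event does not resolve on withdrawal.

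Relatedness feeds the safety endpoints. The Protocol Summary and Sections 2.1 and 2.2 list "related AEs, AEs leading to study drug discontinuation, AEs by severity and relatedness", under the primary objective for the MAD part and under the safety objective for the POC part. Section 8.2.5.1 plans a tabulation of treatment-emergent AEs by relationship.

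Other sections use different causality thresholds. Section 6.2.2.7.2 uses "reasonable causal relationship with the study drug" for SAEs that come to light after the final visit. Section 6.2.2.7.1 uses "related or possibly related to exposure to investigational product" for infant deaths more than one month after birth. Section 6.2.2.5 defines unexpected serious reactions by association with use of the drug.

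**The concern.** A two-category causality scale works only if the categories cover every event. Here Related is written as near-certainty and Unrelated as near-absence of any time link. Nothing is written for the events between them.

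Those middle events are the ones of interest in this trial. Section 1.2.5 names infection as a risk that follows from the mechanism of action, and Section 1.2.2.3 reports that infections were prominent among the related AEs in the healthy-volunteer study. Patients here have active SLE and background treatment (Section 4.4, criterion 8), so another explanation will often be available where it was not in healthy volunteers. An endpoint defined by relatedness could then miss possible drug effects. It could also vary with how each site resolves a choice that the definitions do not settle.

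**Working it through.** The protocol gives no expected rate of related events, so there is no figure to reproduce. The check is a comparison of the definitions.

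**Step 1: conditions.** Let T be plausible timing, A the availability of another explanation (disease or other drugs), and D a definitive event. Read as written:

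- Related requires T, not A, and D. The withdrawal element is left out because it is worded as an expectation and footnote a allows exceptions.
- Unrelated requires not T. Its other two sentences describe what may be or typically is the case, and are not conditions.

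**Step 2: coverage.** Three yes/no conditions give 2 × 2 × 2 = 8 combinations.

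- Not T: 4 combinations, all Unrelated.
- T, not A, D: 1 combination, Related.
- T with A, or T without D: 8 − 4 − 1 = 3 combinations, which meet neither definition.

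These are logical cells, not frequencies. They show that a gap exists and say nothing about how many events fall in it.

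**Step 3: a concrete event.** A patient taking methotrexate for active SLE develops an infection shortly after a monthly dose. The timing is plausible, so the Unrelated definition fails. The disease or the methotrexate could explain the infection, so the Related definition fails on its no-other-explanation condition, and probably on the definitive one too. A category must still be chosen.

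**Step 4: direction.** Two features of the wording pull such an event towards Unrelated: the mandatory wording in the Related row, and the mention of concomitant disease and other drugs as typical explanations in the Unrelated row. One feature pulls the other way: Unrelated asks for little or no time link. Undercounting is therefore the likelier direction but is not certain. Inconsistent assignment follows either way, because the definitions do not decide the case.

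**Step 5: agreement with other sections.** A reasonable or possible relationship, as used in 6.2.2.7.2 and 6.2.2.7.1, is a lower bar than Table 3's Related row. Table 3 has no category that records it.

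**The case against.** The strongest reply is that the categories are chosen by medical judgment after weighing all contributing factors. An investigator may therefore place a possible drug effect under Related despite the strict wording. That stands. It removes any claim that undercounting is certain, but it does not close the gap, since sites are left to exercise judgment without a usable definition.

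A second reply is that safety capture does not depend on causality. All AEs are recorded (6.2.2.2), SAEs are reported within 24 hours whatever the causality (6.2.2.7.2), and special-interest events, including opportunistic infections, are reported without a relatedness test (6.2.2.7.3). The trial is placebo-controlled and the DMC sees unblinded data. This also stands. It confines the problem to counts based on relatedness, and a reader should not infer that a safety signal would be hidden.

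Third, the phrases in 6.2.2.7.1 and 6.2.2.7.2 are triggers for special reporting situations and do not set the on-study endpoint. That is fair. They show inconsistent standards but are not the main defect.

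Three stronger readings are tempting, and the protocol does not support them.

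- *That withdrawal effects cannot be seen within follow-up.* The half-life is given as "ranging from 80 to 87 days" and the last visit is 90 days after the last dose, so 0.5^(90/80) = 0.459 to 0.5^(90/87) = 0.488 of the drug would remain. But Table 3 defines the response to withdrawal by symptoms, not by drug clearance, and footnote a allows exceptions. Residual drug does not measure misclassification.
- *That every patient takes a steroid or immunosuppressant, so infection can always be explained otherwise.* Criterion 8 in Section 4.4 can be met with an antimalarial alone.
- *That dose escalation was distorted.* Section 3.1.1.2 counts only attributable events as DLTs but does not refer to Table 3. Section 3.1.2.1 says that the safety review for dose selection looked at all AEs, SAEs and special-interest events.

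**Conclusion.** The point holds as a defect in a definition that feeds stated endpoints. Table 3 forces a choice between two categories that do not cover plausibly timed events with another possible explanation, or plausibly timed events that are not definitive. Related-AE counts and the tabulation by relationship may be too low and will be assigned inconsistently across sites.

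The size cannot be derived from the protocol. It depends on how many events fall in the gap and how investigators resolve them, and neither is stated. The conclusion assumes only that investigators give the written definitions some weight. Because assessment is blinded, the rule treats the same event alike in either arm. Comparisons of total AEs, SAEs and special-interest events are intact. The table should be corrected, but the defect does not undermine the safety evaluation as a whole.

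**What to change.** Amend Table 3 so that the two categories are exhaustive: Related means a reasonable possibility that study drug caused the event, and Unrelated means no reasonable possibility. Remove the conditions that nothing else can explain the event and that it be definitive. Align the causality wording in Sections 6.2.2.5, 6.2.2.7.1 and 6.2.2.7.2 with the new definitions.

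Apply the change to the POC part. Have investigators re-assess POC events already recorded while treatment assignment is still blinded. Report MAD relatedness under the existing definition and state the difference in the study report.

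The cost is one table, a few aligned sentences, site retraining and the blinded re-assessment; no visits or patients are added. There are two downsides: more events will be called related in both arms, and MAD and POC relatedness will not be directly comparable.

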6.2.2.5 Seriousness of Adverse Events

An SAE is defined as any untoward medical occurrence that at any dose:

- Results in death
- Is life threatening; this means that the patient was at risk of death at the time of the event; it does not mean that the event hypothetically might have caused death if it were more severe
- Requires hospitalization or prolongation in existing hospitalization
- Results in persistent or significant incapacity or substantial disruption of the ability to conduct normal life functions
- Is a congenital anomaly or birth defect
- Is other important medical event (see below)

Important medical events that do not result in death, are not life threatening, or do not require hospitalization may be considered SAEs when, based on appropriate medical judgment, they may jeopardize the patient and may require medical or surgical intervention to prevent 1 of the outcomes listed in this definition. Examples of such events are:

- Intensive treatment in an emergency room or at home for allergic bronchospasm
- Blood dyscrasias or convulsions that do not result in inpatient hospitalization
- Development of drug dependency or drug abuse

Hospitalization for elective surgery or routine clinical procedures that are not the result of AE (e.g., elective surgery for a pre-existing condition that has not worsened) need not be considered SAEs. If anything untoward is reported during the procedure, that occurrence must be reported as an AE, either 'serious' or 'nonserious' according to the usual criteria.

Suspected unexpected serious adverse reactions (SUSARs) are AEs that are associated with the use of the drug and are serious and unexpected.

6.2.2.6 Adverse Events of Special Interest

AEs of special interest in this study include the following:

1. Anaphylaxis and serious allergic reactions
2. Grades 2 to 5 injection site reaction, including erythema, pain, and induration (see [Appendix 6](#))
3. Drug Induced Liver Injury (DILI) assessed following Hy's Law
4. Malignancy (not including basal cell carcinoma or squamous cell carcinoma of skin)
5. Opportunistic infections such as disseminated histoplasmosis, cryptococcosis, disseminated herpes simplex, disseminated tuberculosis, *Aspergillus* sp., *Candida albicans*, *Coccidioides immitis*, *Cryptococcus neoformans*, *Cytomegalovirus*, *Histoplasma capsulatum*, *Isospora belli*, and *Polyomavirus JC polyomavirus*

6. Cryptosporidiasis

6.2.2.6.1 Anaphylaxis and Serious Allergic Reactions

Anaphylaxis will be defined according to the National Institute of Allergy and Infectious Diseases/Food Allergy and Anaphylaxis Network (NIAID/FAAN) criteria.⁴² In the event of anaphylactic reaction or severe/serious hypersensitivity/allergic reaction, the patient must discontinue IP and emergency resuscitation measures implemented. In case of other mild to moderate hypersensitivity reaction, depending on the severity, the Investigator may manage in accordance with the standard-of-care.

Anaphylaxis is highly likely when any one of the following 3 criteria is fulfilled:

- Acute onset of an illness (minutes to several hours) with involvement of the skin, mucosal tissue, or both (e.g., generalized hives, pruritus, or flushing, swollen lips-tongue-uvula) and at least 1 of the following:
 - a. Respiratory compromise (e.g., dyspnea, wheeze-bronchospasm, stridor, reduced peak expiratory flow [PEF], hypoxemia)
 - b. Reduced blood pressure or associated symptoms of end-organ dysfunction (e.g., hypotonia [collapse], syncope, incontinence)
- Two or more of the following that occur rapidly after exposure to a likely allergen for that patient (minutes to several hours):
 - a. Involvement of the skin-mucosal tissue (e.g., generalized hives, itch-flush, swollen lips-tongue-uvula)
 - b. Respiratory compromise (e.g., dyspnea, wheeze-bronchospasm, stridor, reduced PEF, hypoxemia)
 - c. Reduced blood pressure or associated symptoms (e.g., hypotonia [collapse], syncope, incontinence)
 - d. Persistent gastrointestinal symptoms (e.g., crampy abdominal pain, vomiting)
- Reduced blood pressure after exposure to known allergen for that patient (minutes to several hours):
 - a. Systolic blood pressure of less than 90 mm Hg or greater than 30% decrease from the patient's baseline

6.2.2.6.2 Injection Site Reactions

Injection site reactions are to be captured and reported as AEs. These will include Grades 2 to 5 injection site erythema, pain, and induration (see [Appendix 6](#)), which are also captured as Adverse Events of Special Interest (see [Section 6.2.2.6](#)). The Investigator should provide a clear description of the observed or reported AE including location and severity. All concomitant treatments used to treat injection site reactions should be recorded and captured in the eCRF, together with the AE of injection site reactions.

